5.2 Recruitment Methods

1. VAST Implementation

No patient or staff populations are being recruited for this portion of the study. Rather, recruitment is at the level of VA Medical Centers. The process for recruiting VA Medical Centers is through existing professional relationships and networking as well as phone calls, emails, and teleconferencing.

We anticipate recruiting up to 10 VA Medical Centers and up to 10 ID experts to work with those sites.

2. Staff Perceptions

VAST members will be approached by email and asked to participate in a semi-structured interview conducted by a research team member distinct from those involved directly in VAST meetings. Additionally, VAST members will be asked to complete a survey using VA REDCap. VAST members will receive an email to their VA email account with a link to the survey and a brief explanation of the survey. After the initial survey email invitation, study staff will send up to 5 follow-up email reminders for completion of the survey.

None of the staff who participate in the VAST or the ID Experts will receive any payments as the activities related to this work pertain to their usual work activities.

3. Evaluation of clinical activities

This study activity will involve reviewing the medical records of Veteran patients discussed during the VAST. Patients will not be recruited for participation.

4. Facility-Level Antibiotic Use

Antimicrobial use data will be extracted from the VA CDW. Veteran data will be used to collect information about antibiotic use, but patients will not be recruited for participation.

5.3 Informed Consent Procedures

1. VAST Implementation

This study activity involves establishing a VAST at each participating site and does not require informed consent.

2. Staff Perceptions

VAST members will be asked to complete a survey using VA REDCap. VAST members will receive an email to their VA email account with a link to the survey and a brief explanation of the survey. Participation in the survey will indicate consent.

VAST members will be approached by email and asked to participate in a semi-structured interview conducted by a research team member distinct from those involved directly in VAST meetings. We have requested that participants may offer verbal consent to participate in semi-structured interviews, and offer verbal consent to audio record the interviews. We choose this approach to avoid generating informed consent documents that would become the only written link between providers and the research data.

Verbal informed consent will be obtained by trained study staff in a private setting. VAST members will be given the opportunity to ask questions before consenting to participate in semi-structured interviews.

3. Evaluation of clinical activities

In order to conduct chart review and obtain information from the CDW, we will request a waiver of informed consent.

4. Facility-Level Antibiotic Use

In order to obtain information from the CDW, we will request a waiver of informed consent.

5.4 Inclusion/Exclusion Criteria

All sites participating in the VAST will be included. Veteran patients will be discussed during VAST calls according to clinical need. Additionally, administrative data will be collected from CDW within the VINCI environment and will be used to extract and analyze age, gender, race/ethnicity, and comorbid conditions for creation of the quarterly Antibiotic Use Reports.

1. VAST Implementation

All participating sites will be included.

2. Staff Perceptions

All staff who participate in the VAST will be invited by email to participate in a survey and a 20-60 minute telephone semi-structured interviews.

3. Evaluation of clinical activities

All patients discussed during the VAST will be included.

4. Facility-Level Antibiotic Use

Information will be collected from CDW for all participating sites.

5.5 Study Evaluations

1. VAST Implementation

Randomization

To randomize rural VAMCs, we will use a matched pairs design to ensure that the total number of acute and long-term care beds is similar between the two study arms. For simplicity, if more than one rural VAMC forms a VAST with the same off-site ID expert, (e.g., both Altoona and Erie have a relationship with the Pittsburgh VAMC) we will randomize both rural VAMCs into the same arm.

VAST Members & Activities

Staff from acute (hospital) and long-term care (CLC) units will populate the team, with the intent of using more than one person with the same role to allow for fluidity among individual members. Each VAST will identify 2 to 3 champions, likely pharmacists and infection preventionists, with responsibilities that include identifying patients prescribed antibiotics and recording the VAST's recommendations in the electronic medical record. Contributions of the ID physician will include his or her clinical knowledge and experience with antimicrobial stewardship. The ID physician will identify 1-2 other individuals, such as an ID-trained clinical pharmacist, to also participate in the VAST. This will enhance continuity of the VAST during holidays, vacations, and travel. Each team will also include a field research assistant for the ID expert(s); field research assistants will help support VAST implementation and data collection.

The VAST will meet for one hour each week. As a whole, team members from the rural VAMC and off-site ID experts will participate in chart review, discussion, and making recommendations regarding the need and choice of antimicrobial agent(s), length of therapy, orders for and interpretation of microbiological cultures and diagnostic tests. At each session, the field research assistant will note the names, roles, and practice setting for each of the VAST participants; this information will be shared with the primary research team.

When feasible, the ID expert(s) will travel to the rural VAMC for a face-to-face kickoff meeting. This will facilitate team building and help set the tone for the ensuing videoconferences. Leadership support to allow time for personnel from the rural as well as the ID expert(s) VAMCs to actively engage in the VAST will be a key factor for success. Further, the presence of Chiefs or Assistant Chiefs of Staff, Medicine, Nursing, and Pharmacy from the rural VAMC, especially at the first 4 to 8 VAST sessions, will help engage other clinical staff.

Implementation Guide and Facilitation

The champions and ID experts will receive an implementation guide that details setting up a SCAN-ECHO clinic specific for the VAST, lays out

general recommendations for a site visit as the initial VAST session, and describes the general process for videoconference sessions.

During facilitation calls, the primary research team will review process maps (Figure 2) with champions at the rural VAMC, field research assistants, and ID experts.

- As sites adapt the intervention to suit their needs, research coordinators will work with each VAST to adjust the process maps for their site, adding or removing components as needed while also making sure each VAST retains the elements necessary for workload capture and program evaluation.
- The process maps will help the research team identify the range of adaptations used by the different VASTs as they tailor the intervention to their sites. The process maps will also help teams that are struggling to identify specific steps leading to limited success and then to develop strategies to overcome barriers.
- Once each VAST indicates it is well-established, which we expect will be around 4 months after their first session, we will re-assess the process maps quarterly and conduct a final review at the conclusion of the intervention period.

Field research assistants will use data collection forms to record and submit quantitative data describing VAST sessions and cost data. The primary research team will assess qualitative aspects of implementation and sustainability. With each facilitation call, whether scheduled or ad hoc, members of the primary research team will use field notes to log barriers and facilitators related to implementation.

2. Staff Perceptions

- a. We will conduct semi-structured interviews of the champions(s) at the rural VAMC and the ID expert(s). These will begin after their VAST is well-established, likely after 4 to 6 months. We will ask interviewees about specific goals or objectives decided on by their VAST and the rationale for those.

Champion(s) from the rural VAMCs (2-3 per site) and ID experts (1-3 per site) will be approached by a member of the research team by email to schedule a 20 to 60-minute telephone interview. The interviews will be digitally recorded, transcribed and analyzed using Atlas.ti (Scientific Software Development GmbH; Berlin, Germany). Inductive and deductive content analysis will be used to identify salient themes, with deductive codes based on domains from SEIPS 2.0 with the additional theme of practice change.

- b. To assess user perceptions, a survey will be deployed and sent to anyone who participated in at least one VAST session. The survey will be developed and deployed using VA REDCap and distributed via VA email. The survey will query perceptions of the VAST in regard to timeliness of recommendations, access to input, influence on the quality of antibiotic use, and overall effect Veterans' care. For rural VAMCs

randomized to the VAST+, additional questions will address respondents' general perceptions of the Antibiotic Use Report as well as its potential role in helping to guide VAST activities.

3. Evaluation of clinical activities

Clinical activities will be assessed by the field research assistants and the primary research team. Field research assistants will record the infectious diagnosis discussed and determine the acceptance of recommendations made by the VAST which the primary research team will validate using administrative data. To describe the clinical activities of each VAST, the field research assistants will use a Case Report Form to record the patients discussed, their diagnoses, the recommendations made, and the acceptance of those recommendations. Field research assistants will upload their Case Report Form to a shared research drive which will be reviewed by the primary research team. For a subset of patients, the primary research team will use chart review to assess the concordance of recommendations made by each VAST with evidence-based clinical practice guidelines.

4. Facility-Level Antibiotic Use

Antimicrobial use data will be extracted from the VA CDW, which permits attribution of medication administration to specific units. The champions at each intervention site will provide their field research assistant with names for acute and long-term care units. We use four metrics to quantify changes in antibiotic use and will use them to assess changes in antibiotic use in acute care as well as well as the long-term care settings.]

1. The first metric, days of antibiotic therapy per 1000 days of care (DOT/1000 DOC), measures the overall rate of antibiotic use and is a common metric that accounts for dose adjustments, including for people who receive dialysis. Administration of any dose of an antimicrobial on a given day represents a single DOT for that agent, regardless of the number of times the doses are administered or the dose strength.
2. Second, we will specifically examine the rate of broad-spectrum antibiotics, defining broad-spectrum agents as those with an Antibiotic Spectrum Index (ASI) score of ≥ 8 . This scale ranges from 1 to 13.
3. The third metric is the rate of antibiotic starts (new prescriptions), calculated as the number of starts per 1000 DOC.
4. The fourth metric is the length of antibiotic therapy in days.
 - a. For people on hemodialysis, up to 72 hours may occur between doses of specific agents (e.g. vancomycin, aminoglycosides, several cephalosporins); these will be considered as a single course.

For each site, we will calculate these statistics at monthly intervals for the 12 months prior to and the 15 months following the first VAST session, allowing for a 3-month wash-in period, to generate descriptive summaries of changes in acute care and in long-term care over time, understand month-to-month variability in these metrics, and to flag any issues with data availability or validity in the course of the

intervention given operational shifts occurring at facilities around COVID-19 treatment or the rollout of the Cerner electronic medical record across the VA.

Additionally, we will use CDW data to determine the antibiotic prescribing patterns for respiratory tract infections and urinary tract infections (UTI) at VAST sites beginning January 1, 2019. We will then conduct a thorough medical record review on patients identified using CDW. Using this data, we will explore system factors, including prescriber specialty, to predict the rate of prescribing of antibiotics by race and ethnicity.

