For this study activity, the study population will be comprised of individuals who participate in the VAST and will include VA staff members. The team members from the intervention sites will include pharmacists, infection preventionists, nurses, and prescribing clinicians. These staff are important antibiotic stewardship stakeholders. Each rural VAMC will pair with an ID expert from another VA facility to form a multidisciplinary VAST which will perform antimicrobial stewardship activities. The rural VAMCs and their affiliated ID physician will be randomized to either the VAST alone (VAST-) or VAST + feedback (VAST+), consisting of a quarterly Antibiotic Use Report describing facility level antibiotic use.

3. Evaluation of clinical activities

For this study activity, VA patients discussed during each VAST will make up the study population. Study staff will perform medical record review and utilize the VA's administrative databases to collect information about the patients. Veteran patients will not be involved in any study interventions; only chart review will be conducted.

4. Facility-level antibiotic use

We will review total antimicrobial use at the intervention sites and at control sites. These data will be accessed via VINCI.

Protection Against Risk

This is a minimal risk study. The primary risk is breach of confidentiality for patients discussed by the VAST and breach of privacy for providers who participate in semi-structured interviews.

1. VAST Implementation

For this study activity, there is no risk to patients or staff.

2. Staff Perceptions

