5.6 Data Analysis

1. VAST Implementation

The primary research team will assess qualitative aspects of implementation and sustainability. With each facilitation call, whether scheduled or ad hoc, members of the primary research team will use field notes to log barriers and facilitators related to implementation. The research team will use process maps to record adaptations. Changes from the initial map will be categorized as major or minor. Further, the number of weeks each VAST required to achieve their final process map will be noted. Together, these assessments will be used to assess fidelity of implementation and to transform the Implementation Guide into a final, robust Implementation Playbook.

2. Staff Perceptions

Once the intervention period for all VASTs is complete, we will assess for differences in the VAST- vs VAST+ arms on perceived influences on Veteran care, proportion of VAST recommendations accepted, and the user experience survey.

3. Evaluation of clinical activities

Characteristics of each facility including number of beds, number of CLC beds, medical complexity group, attendance of leadership at VAST sessions and the mean number of cases discussed per session will also be compared. If significant differences are seen between VAST- and VAST+ sites, additional multivariable analyses will be conducted.

4. Facility-Level Antibiotic Use

To assess for impact of VAST on antibiotic use, we will summarize the 4 antibiotic use metrics for each site, comparing the pre- and post-implementation periods for the acute and long-term care units. Rates of overall antibiotic use (DOT/1000 DOC), broad-spectrum antibiotic use (DOT/1000 DOC) and antibiotic starts (new prescriptions/1000 DOC) will be calculated with 95% confidence intervals based on exact Poisson distributions. To summarize length of therapy in the pre- and post-implementation periods, we will calculate means and 95% confidence intervals.

To assess for differences between the VAST- and VAST+ study arms, we will use a multi-level Poisson regression model in which facilities will be

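### Sites that share an ID expert are randomised together, but the VAST+ versus VAST- model has no level for the expert, so precision is overstated wherever an expert is shared

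*Combined protocol and SAP*

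**What the plan says.** **Allocation.** Section 5.1 (Study Population, Staff perceptions) states: "The rural VAMCs and their affiliated ID physician will be randomized" to one of the two arms. Section 5.5 (Randomization) adds that "we will use a matched pairs design to ensure that the total number of acute and long-term care beds is similar" in the two arms, and that "if more than one rural VAMC forms a VAST with the same off-site ID expert", then "we will randomize both rural VAMCs into the same arm". It gives two rural centres linked to one larger centre as an example.

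**Numbers.** Section 5.2: "We anticipate recruiting up to 10 VA Medical Centers and up to 10 ID experts to work with those sites". Section 5.1 sets a minimum of one site per expert and no maximum.

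**Aim 3 analysis.** Section 5.6 (Facility-Level Antibiotic Use) uses a "multi-level Poisson regression model in which facilities will be" random effects, with arm, time and their interaction as fixed effects. Length of therapy gets a model of the same form. No expert level, matched-pair term, robust variance or small-sample correction is described.

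**Aim 2 analysis.** Section 5.6 (Staff Perceptions) will compare the arms on "perceived influences on Veteran care, proportion of VAST recommendations accepted" and the user survey. It names no test, unit of analysis or clustering adjustment.

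**The concern.** The off-site expert's team is the active part of the intervention: it advises weekly on whether to treat, with what and for how long. Two sites with the same expert receive advice of the same style and are always in the same arm. Their pre/post changes are therefore likely to be positively correlated, and the correlation does not average out between arms. A model that recognises only facilities counts such sites as separate pieces of evidence about the report's effect. With at most 10 sites, there are few units to absorb this. The contrast at stake is the randomised comparison on the primary outcome, overall antibiotic use, and on the secondary antibiotic metrics.

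**Working it through.** **Inputs.** Up to 10 sites and up to 10 experts (section 5.2). The plan states no power, alpha, effect size or intraclass correlation, so there is no figure to reproduce. Assumed here: 10 sites, a two-sided 5% test, and ρ, the share of variance in log pre/post change that lies between experts, from 0.1 to 0.7.

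**Model for the check.** Site change = √ρ × (expert effect) + √(1−ρ) × (site effect), with no arm effect. The site effect gives each facility its own change, so the facility-by-time gap is already repaired and only the expert level is being tested.

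**Hand calculation for one case.** Take five experts with two sites each, split 3 to 2 (6 sites versus 4), and ρ = 0.5. Let an arm have n sites and p ordered pairs of sites with the same expert.
- True variance of an arm mean, in units of the site variance: (n + pρ)/n². The difference has variance (6 + 3)/36 + (4 + 2)/16 = 0.250 + 0.375 = 0.625.
- Expected within-arm sum of squares: (n − 1) − pρ/n. This gives (5 − 0.5) + (3 − 0.5) = 7, so the pooled variance is 7/8 = 0.875.
- Variance the facility-level test believes: 0.875 × (1/6 + 1/4) = 0.365.
- Ratio 0.625/0.365 = 1.71, so the standard error is understated by √1.71 = 1.31.
- The critical value 2.306 (8 df) then acts like 2.306/1.31 = 1.76, a type I error of about 12%.

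**Simulation.** 40,000 null trials per case (Monte Carlo standard error 0.1 to 0.2 points). Type I error of the facility-level t-test:

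| Sharing among 10 sites | ρ = 0.1 | 0.3 | 0.5 | 0.7 |
|---|---|---|---|---|
| None (10 experts) | 5% | 5% | 5% | 5% |
| One shared (9 experts) | 5.2% | 5.6% | 6.3% | 6.8% |
| One shared per arm (8) | 5.5% | 6.4% | 7.3% | 8.7% |
| Three shared (7) | 5.8% | 7.1% | 8.9% | 11.2% |
| All shared (5) | 6.3% | 9.1% | 12.4% | 16.7% |

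The t-test on expert means stays between 4.5% and 5.1%.

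**Relation to the facility-by-time gap.** If the random effects in section 5.6 are intercepts only, they largely cancel from the arm-by-time contrast. With an assumed 3,000 days of therapy per site-year and no shared expert, the type I error of that model is 0.37 when true log changes vary between sites with SD 0.05, and 0.62 to 0.63 with SD 0.10. Two shared experts per arm at ρ = 0.5 raise these to 0.44 and 0.68. Adding facility-by-time variation removes the first problem and leaves the inflation in the table.

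**Aim 2, only if responses were pooled as independent.** The design effect is 1 + (m − 1) × ICC. Ten respondents per unit and an assumed ICC of 0.05 to 0.10 give 1.45 to 1.9. For recommendations, 50 per site at ICC 0.01 gives √1.49 = 1.2 and 200 per site at ICC 0.05 gives √10.95 = 3.3 as the factor by which the standard error is understated. Every input is assumed, and this is mostly clustering within a site, not the expert level.

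**The case against.** The strongest reply is that the problem is conditional. The same-arm rule opens with an if, the plan allows as many experts as sites, and the only example is one pair of centres. With one expert per site, facility and randomised unit coincide and the effect is zero. Parts of the protocol not in the text reviewed, apparently including section 4.0, may list the pairings. This stands, so no single figure can be given and no loss of degrees of freedom can be stated as fact. It does not remove the point: the plan foresees sharing and writes an allocation rule for it, but no matching analysis.

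Second, the inflation is modest for light sharing or low correlation, and it is second to the facility-by-time gap. Both are true. Repairing the larger gap does not repair this one.

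Third, a reader might infer that Aim 2 treats individual responses or recommendations as independent. The text does not say so; it leaves the unit open.

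Fourth, a reader might infer that the same-arm rule contradicts the matched-pairs scheme. Two linked sites cannot be each other's match, but they can be matched to other sites or as a block. Section 5.5 does not say which, so this is an unspecified detail and not a contradiction.

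**Conclusion.** The point holds in conditional form. Where an expert serves more than one site, allocation is by expert, the Aim 3 model ignores that level, and standard errors for the arm-by-time contrast are too small if linked sites change alike. For 10 sites, a nominal 5% test and an assumed correlation of 0.1 to 0.7, true type I error runs from about 5% with one shared expert and low correlation to about 17% with all five experts shared and high correlation. It stays at 5% with no sharing. The extent of sharing and the correlation are assumptions, since the text available gives neither. For Aim 2 the finding is only that the unit and any clustering adjustment are unspecified. This should be settled before any arm comparison is run, together with the facility-by-time variation, which matters more.

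**What to change.** In section 5.6, define the randomised unit as the ID expert plus all linked sites, and use it for every VAST+ versus VAST- contrast. Prespecify one of two analyses:
- one pre/post change per unit, with small-sample degrees of freedom that match the allocation (units minus 2 if unpaired, pairs minus 1 if paired); or
- a randomisation test that follows the allocation actually used, including its pairs.

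Use the same unit for the Aim 2 survey and acceptance comparisons. Report the number of sites per expert in each arm. If allocation has not been done, form the matched pairs from these units on summed beds and say what happens to an odd unit. If it has been done, only the analysis changes.

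**Cost.** SAP wording, and fewer degrees of freedom where experts are shared. Unpaired, 10, 8, 7 or 5 units give 8, 6, 5 or 3 df and critical values of 2.306, 2.447, 2.571 or 3.182. Five pairs give 4 df and 2.776. The randomisation test has a floor: with 5, 4 or 3 pairs the smallest two-sided p is 2/2⁵ = 0.0625, 2/2⁴ = 0.125 or 2/2³ = 0.25. It could not reach 5% with five pairs or fewer, and that should be known before it is chosen. Random effects at both expert and facility level may be poorly identified with five to seven experts, so the unit-level summary is safer. If no expert is shared, the expert-linked unit is simply the facility and the choice of unit costs nothing.

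### Acceptance and guideline concordance are judged by staff who help deliver the VAST, with no stated masking or rule for choosing the chart subset

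*Combined protocol and SAP*

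**What the plan says.** All references are to the combined protocol and SAP.

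- **Assessors.** Section 5.5, item 3 (clinical activities): "Clinical activities will be assessed by the field research assistants and the primary research team". The field research assistants "determine the acceptance of recommendations made by the VAST which the primary research team will validate using administrative data".
- **Concordance.** Same item: "For a subset of patients, the primary research team will use chart review to assess the concordance of recommendations made by each VAST" with guidelines. It does not say how the subset is chosen, how many reviewers read each chart, or whether they know the arm.
- **The assessors' part in delivery.** Section 5.5, item 1 places a field research assistant on each team, and "field research assistants will help support VAST implementation and data collection". Of the other assessor it says: "During facilitation calls, the primary research team will review process maps (Figure 2) with champions at the rural VAMC, field research assistants, and ID experts".
- **Use of the results.** Section 5.6, under Staff Perceptions, compares the share of recommendations accepted between VAST- and VAST+. It does not list concordance there. Section 3.0 puts concordance under Aim 2, which concerns the VAST overall and VAST+.
- **Interviews.** Section 5.2 has them "conducted by a research team member distinct from those involved directly in VAST meetings". Section 5.5 has no such separation for chart review or acceptance.

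**The concern.** Both measures need some judgement. Section 5.5 has the VAST advise on whether an antibiotic is needed, which one, for how long, and how to order and interpret cultures and tests. Administrative data can confirm that a drug was stopped or switched. They are unlikely to settle whether advice was partly followed, or whether advice on reading a culture was taken up. Concordance with a guideline rests on a reviewer's reading of the chart, and no administrative check is described for it.

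If the person making such calls knows the arm and has helped the site run the intervention, the calls may lean without intent. A subset chosen without a stated rule adds a second route by which knowledge of the arm could enter. At stake is whether a difference between VAST- and VAST+ on these two measures could be told apart from assessor expectation. Reviewing more charts would not help, because this is bias and not sampling error.

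**Working it through.** The plan gives no sample size, expected rate or power for acceptance or concordance, so there is no figure to reproduce. The check sets the sections side by side and then illustrates the size.

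**1. Do the assessors know the arm?** The text does not say so directly. The field research assistant is part of a VAST that either receives the quarterly Antibiotic Use Report or does not. The primary research team facilitates the sites, of which there are at most 10 (section 5.1), and section 2.0 says the study's team developed the report. Knowledge of the arm is an inference from these roles, but a strong one unless a masking procedure is stated.

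**2. Would the chart reveal the arm?** Not necessarily. Both arms hold VAST sessions and record recommendations in the medical record (section 5.5). They differ by a facility-level report sent to the team (section 5.1), which is not described as a chart item. The facility name, however, gives the arm away to anyone who knows the allocation. Masking is therefore feasible, but it requires withholding the allocation and, as far as possible, the site.

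**3. How exposed is each measure?**

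| Measure | Assessor | Objective check | Compared by arm? |
|---|---|---|---|
| Acceptance | Field research assistant on the VAST | Administrative data, applied by the primary research team; no rule for disagreements | Yes, section 5.6 |
| Concordance | Primary research team | None stated | Implied by Aim 2; not named in section 5.6 |

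The measure with the explicit arm comparison has the objective check. The measure with no such check has only an implied comparison.

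**4. Illustrative size.** Let *b* be the share of records needing judgement and *t* the difference between arms in the probability that such a record is called favourably. With no true difference between arms, the spurious difference is *d = b × t*. None of the inputs comes from the documents.

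- *b* = 0.20, favourable calls 60% in VAST+ and 40% in VAST-: *d* = 0.20 × (0.60 − 0.40) = 0.04, or 4 points.
- Low end, *b* = 0.10 and *t* = 0.10: *d* = 0.01, or 1 point.
- High end, *b* = 0.30 and *t* = 0.30: *d* = 0.09, or 9 points.
- No lean, *t* = 0: *d* = 0.

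A false-positive rate is not offered as a finding. It would need the number of records per arm and the clustering by site, and the plan gives neither for these measures.

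**The case against.** The strongest reply has four parts.

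- **The exposure is narrow.** Acceptance is validated against administrative data, and concordance is not among the arm comparisons in section 5.6. This stands. It limits the point to concordance and to the acceptance calls that those data leave open.
- **No leaning is shown.** A reader might infer that the team has declared an expectation that VAST+ will do better on these measures. The documents do not support that. Aim 2 states a direction only for perceived influence on care, Aim 3 only for antibiotic use, and the central hypothesis is general. A reader might also take 1 to 9 points as an estimate of the bias. It is not: the range leaves out zero lean by construction.
- **Duties may already be divided.** The personnel and resources sections (1.0 and 4.0) are not in the public text, so a division of duties within the primary research team cannot be excluded. This stands as a limit on certainty. Section 5.5 still assigns the work to the team as a whole.
- **The interview rule is a weak precedent.** It separates interviewers from VAST meetings, and section 7.0 treats interview handling as a privacy matter. It does not mask the arm, and a facilitator who attends no VAST meeting could satisfy it. This stands, so copying that rule would not be enough. What it does show, with section 7.0 limiting interviews to certain members of the primary team, is that work can be divided within that team.

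**Conclusion.** The point holds as a design weakness in two Aim 2 measures. Staff who take part in delivery determine acceptance and judge concordance, and neither masking nor a subset-selection rule appears in the available text. Concordance and the acceptance calls that administrative data cannot settle are the exposed parts.

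A reader might infer that all Aim 2 comparisons, or the trial's main result, are compromised. The documents do not support that. Perceptions and user experience are reported by VAST members themselves, which is a separate matter. The primary and secondary antibiotic-use outcomes of Aim 3 come from Corporate Data Warehouse records and are untouched.

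The size cannot be derived from the plan. The conclusion rests on two assumptions: that people in these roles know the arm, and that some records need judgement. The change is worth making because it is cheap, not because a bias has been demonstrated.

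**What to change.** Amend section 5.5, item 3, as follows.

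1. Concordance review, and adjudication of acceptance calls that administrative data do not settle, are done by existing team members who run no facilitation calls, prepare no Antibiotic Use Reports and are not given the allocation.
2. As far as feasible they work from extracts under the study-specific identifier, with the facility name and any mention of the report removed.
3. The chart subset is drawn by a seeded random procedure within site and diagnosis. It is run by someone who does not work with the VASTs, which rules out the research coordinators who adjust the process maps with each team.
4. The field research assistant's call is kept as the first entry.

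The same amendment should settle what is being judged: section 3.0 speaks of the concordance of clinical care, section 5.5 of the concordance of VAST recommendations.

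**Cost.** No additional reader, provided the team has members who fit the first item; that cannot be verified from the public text. Preparing extracts is new work, because section 5.1 expects identifiable information to be needed for chart review, so someone with that access must do the redaction. Masking will be imperfect where a note names the facility or cites the report. If no suitable team member exists, the protocol should say so and report both measures as assessed by unmasked staff.
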